**3. Provide a justification for the sample size used in this protocol.**

Include sample size calculations or statistical power estimation. If not applicable, please provide explanation.

Also include the anticipated accrual rate, the accrual goal for the study, including accrual goals by strata if appropriate, adjustments for drop-outs etc. and study duration.

Answer/Response:

The first row of Table 1 provides the minimum detectable within-intervention changes in the composite Fugl-Meyer Upper Extremity (FMUE) scores that would lead 80% of the time to rejecting the null hypothesis, listed according to patient retention rate. The second row of Table 1 provides the minimum detectable between-intervention difference. Note that accounting for a 20% dropout rate, recruitment of a total of 40 subjects provides sufficient power to detect a pre- to post-intervention change of 2.4 units, a value that is consistent with previous studies of hand therapy interventions [60].

**Table 1. Phase II power analysis**

comparison type	Phase II Study Patient Retention Rate % (n)				
	100% (20)	95% (19)	90% (18)	85% (17)	80% (16)
within-intervention	1.5	1.5	1.6	1.6	1.7
between-intervention	2.1	2.2	2.2	2.3	2.4

#### **4. What is your plan for primary variable analysis?**

Include primary outcome(s)/predictor variable(s), statistical methods/models/tests to be employed, or descriptive summaries as appropriate. If not applicable, please provide explanation.

Answer/Response:

The pre- to post-intervention change in the composite FMUE score will be the primary endpoint for the Phase II efficacy study. Each of the seven tasks in the hand portion of the FMUE will be scored on a scale of 0 to 2 [53] and summed to produce a composite score. The pre-intervention scores will be subtracted from the post-intervention scores to produce a set of delta values. These delta values scores ( $\Delta$ ) will be analyzed via Analysis of Covariance (ANCOVA). One null hypothesis will test if the mean pre- to post-intervention change in the composite FMUE score is equal to zero, while the second null hypothesis will test if the mean pre- to post-intervention change in the composite FMUE score is the same for patients who undergo 8-weeks of GRASP therapy and patients who undergo 8 weeks of intensity-balanced standard care. For both null hypotheses, a  $p \leq 0.05$  decision rule will be utilized as the rejection criterion.

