**Hypotheses**

- Use of GRASP for UE practice in a Home Exercise Program (HEP) will improve motor function in a cohort of adult stroke patients
- Subjects assigned to the GRASP HEP will experience improved motor function compared to those assigned to a Usual Care Treatment (UCT) group
- GRASP will be found to be usable and well-accepted by participants who have sustained a stroke.

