**2. What are the statistical considerations for the protocol?**

The objectives section and the statistical section should correspond, and any objective for which analysis is unfeasible should be deleted. Also, the estimates and non-statistical assumptions of the statistical section should be supported by discussion in the background section.

The answer to this question should include:

- Study Design/Endpoints
- Recap of study objectives and endpoint definitions. An assessment of how study objectives will be assessed by identifying & defining which endpoints will be used to assess each component of the study objectives.
- The study design should include contingencies for early stopping, interim analyses, stratification factors (if applicable), and any characteristics to be incorporated in analyses.
- The power/precision of the study to address the major study endpoint(s), the assumptions involved in the determination of power/precision.
- If statistical hypothesis testing is included then specify the null and alternative hypotheses, the test statistic, and the type I and II error rates
- If precision of an estimate, then provide a definition for precision
- If other, then specify

Answer/Response:

Following an initial visit (in outpatient clinic) for consent administration and screening, participants will be asked to return for a pre-assessment visit involving a battery of gold-standard UE function tests including: the Fugl-Meyer assessment of UE motor function (FMUE); the Wolf Motor Function Test (WMFT) assessment of UE motor function; the Box and Blocks Test; and the Motor Activity Log (MAL). Permuted block randomization will be employed. Subjects assigned to GRASP HEP will be asked to employ the GRASP system for UE practice at home over an 8-week period. Patients in the UCT group will not receive any treatment through the study and will continue to receive any previously prescribed therapy services. After 8 weeks, all participants will be asked to return for a post-assessment visit repeating the same battery of tests. Additionally, subjects will be asked to respond to a set of questionnaire-based instruments including the System Usability Scale (SUS); a technology acceptance model (TAM) questionnaire; and a Player Experience of Needs Satisfaction (PENS) questionnaire; and participate in a structured interview.

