The pre- to post-intervention change in the composite assessment scores will be the primary endpoint for the GRASP Phase II study. Pre-intervention scores will be subtracted from post-intervention scores to produce a set of delta values which will be analyzed via Analysis of Covariance. One null hypothesis will test if the mean pre- to post-intervention change in scores is equal to zero, while the second null hypothesis will test if the mean pre- to post-intervention change in scores is the same between groups. For both null hypotheses, a  $p \leq 0.05$  decision rule will be utilized as the rejection criterion.

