#### **GROUP 2: UCT GROUP:**

[figure not shown]
- Participants in the control group will continue to receive any previously prescribed therapy services. These patients will not receive any treatment services through the study as UCT group participants.
- At least once every two weeks during the 8 week period, non-blinded study staff will contact the participant by phone or HIPAA compliant video conferencing to collect self-reported adherence data and confirm that no change in medical status has occurred that would impact continued participation.

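### The primary FMUE analysis has two unranked tests at p ≤ 0.05, and the one matching Hypothesis 1 has no control, so change shared by both arms could be reported as a GRASP benefit

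*Combined protocol and SAP*

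**What the plan says.** Statistical Considerations, item 4 (primary variable analysis) makes the pre-to-post change in composite FMUE the primary endpoint, analysed by ANCOVA, with two null hypotheses:

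- **Null 1:** "One null hypothesis will test if the mean pre- to post-intervention change in the composite FMUE score is equal to zero". No arm is named.
- **Null 2:** the mean change is the same in the two arms. In item 2 (statistical considerations) the wording is "the second null hypothesis will test if the mean pre- to post-intervention change in scores is the same between groups".

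Both items apply p ≤ 0.05 to each null. Neither ranks them, makes one conditional on the other, divides the error rate, or says which rejection supports an efficacy claim. Item 5 applies the same method to WMFT, Box and Blocks and MAL.

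The Hypotheses section has two statements on motor function. The first is "Use of GRASP for UE practice in a Home Exercise Program (HEP) will improve motor function in a cohort of adult stroke patients". The second is "Subjects assigned to the GRASP HEP will experience improved motor function compared to those assigned to a Usual Care Treatment (UCT) group".

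Item 3 (sample size) gives each test its own row in Table 1. At 16 per arm the detectable value is 1.7 units within an arm and 2.4 units between arms. The text then says that "recruitment of a total of 40 subjects provides sufficient power to detect a pre- to post-intervention change of 2.4 units".

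The control arm is described in two ways. Item 4 has it as "patients who undergo 8 weeks of intensity-balanced standard care". Item 2 says "Patients in the UCT group will not receive any treatment through the study and will continue to receive any previously prescribed therapy services", and the UCT section of Study Procedures says "These patients will not receive any treatment services through the study as UCT group participants".

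**The concern.** A one-arm test of zero change cannot separate the effect of GRASP from anything else that moves the score over eight weeks. The protocol leaves three such sources open. Previously prescribed therapy continues in both arms (GRASP HEP Independent Practice; UCT group). The same battery is repeated at the final visit. The eligibility criteria set no time since stroke, and recruitment covers current and former stroke patients, so spontaneous recovery is not excluded.

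The second hypothesis maps to null 2. The first names no comparator, so only null 1 maps to it, yet its wording is causal. A report that follows the plan could reject null 1, declare the first hypothesis confirmed, and state that GRASP improves motor function while the randomised comparison shows nothing.

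Two other passages blur which test decides. The sample size text calls 2.4 units a pre-to-post change, although in Table 1 it is the between-arm value. The comparator in null 2 also does not match the description of the control arm elsewhere.

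**Working it through.** **Inputs from the documents:** 40 randomised 1:1; 20% dropout, so 40 × 0.80 = 32, or 16 per arm; 80% power; p ≤ 0.05 for each null; the ten cells of Table 1.

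**Inputs not in the documents:** the SD of change, the sidedness of the tests, and any expected control-arm gain. The SD is back-solved from Table 1, and the gains are assumed.

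**1. Reproduce Table 1.** Take two-sided 0.05 and an error term pooled over the arms (df = 2n − 2). The detectable value is then m × SD/√n within an arm and m × SD × √(2/n) between arms, where m is the noncentral-t multiplier for 80% power.

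- n = 20, m = 2.875, SD = 2.32: within 2.875 × 2.32/√20 = 1.49; between 2.875 × 2.32 × √(2/20) = 2.11. Table 1 has 1.5 and 2.1.
- n = 16, m = 2.895, SD = 2.32: within 2.895 × 2.32/4 = 1.68; between 2.895 × 2.32 × √(2/16) = 2.38. Table 1 has 1.7 and 2.4.

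Any SD from 2.305 to 2.34 reproduces all ten cells. A one-sample t for the within row fits at most eight. A within test that combines both arms fits only five, so Table 1 supports reading null 1 as a one-arm test. A one-sided 0.05 test with SD about 2.62 also fits all ten cells, so sidedness cannot be settled from the table.

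**2. Shared gain, no GRASP effect.** With n = 16 and SD 2.32, the noncentrality for null 1 in the GRASP arm is gain/(2.32/4) = gain/0.58. The lower figure in each range is the one-sample t (df 15), the higher the pooled error term (df 30). The last two columns are from simulation (400,000 runs).

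| Assumed gain in both arms | Noncentrality | Null 1 rejects | Between-arm test rejects | Null 1 favours GRASP, between-arm test does not |
|---|---|---|---|---|
| 0.5 | 0.86 | 13% | 5% | 11% |
| 1.0 | 1.72 | 37–39% | 5% | 34–36% |
| 1.5 | 2.59 | 68–71% | 5% | 65–68% |
| 1.7 | 2.93 | 78–81% | 5% | 76–78% |

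Half of the 5% (2.5%) favours GRASP. The 1.7 row is near 80% by construction, because 1.7 is Table 1's detectable within-arm change.

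**3. Sensitivity.** With SD from 2.0 to 2.7, null 1 rejects 11–16%, 28–49% and 55–83% for gains of 0.5, 1.0 and 1.5. With one-sided 0.05 and SD 2.62, the figures for 0.5, 1.0, 1.5 and 1.7 are 18%, 43–44%, 70–72% and 80–81%.

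**4. No change in either arm.** If either test could support a claim, the chance that at least one favours GRASP is about 4.1%, against 2.5% for the between-arm test alone. For any rejection it is about 8% against 5%.

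Baseline adjustment is not modelled, because the documents name no covariate and give no baseline correlation.

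**The case against.** The strongest reply is that the plan never says either null alone establishes efficacy. It asks two questions and gives each a test. The controlled test is prespecified on the primary endpoint, so its result would appear beside any within-arm result. The randomised design and the 2.4-unit figure behind the sample size already point to the between-arm test. No passage assigns nulls to hypotheses, and the first hypothesis can be read as a modest statement about a cohort.

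The numbers can also be questioned. If both arms truly gain, rejecting zero change is correct, so the percentages in step 2 are power and not false-positive rates. All the gains are assumed. The composite has seven items scored 0 to 2, a maximum of 14, so gains of 1.0 to 1.7 units are about 7–12% of the scale. No passage supports a gain of that size in a control arm given no study treatment.

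Much of this stands. Misattribution is a risk and not a certainty, the percentages are illustrations, and the error inflation is modest. The mismatched 2.4 label and comparator would need correcting even if the nulls were ranked. The reply does not remove the gap, though. The within-arm test is powered in its own row of Table 1 and held to the same p-value rule, so it is more than a descriptive summary. A cohort reading of the first hypothesis makes null 1 its test, while its wording still credits the change to GRASP. No sentence gives the between-arm test priority.

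**Conclusion.** The concern holds and should be fixed. Two tests of the primary endpoint are unranked, and the uncontrolled one can confirm the first hypothesis from change common to both arms. The main problem is attribution: with no GRASP effect, null 1 could reject in about 13% to 71% of trials for assumed shared gains of 0.5 to 1.5 units, while the between-arm test stays at 5%. Error inflation with no change in either arm is secondary (about 4.1% against 2.5% in favour of GRASP).

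The missing ranking is plain from the text. The sizes rest on an SD of 2.32 back-solved from Table 1, 16 per arm, two-sided tests, assumed gains, and null 1 being run in the GRASP arm. If null 1 instead combined both arms, it would isolate GRASP even less.

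**What to change.** - **Items 2 and 4:** state that the between-arm comparison of change in composite FMUE is the sole primary test at p ≤ 0.05, say whether it is two-sided, and say that it alone supports an efficacy claim. Report within-arm mean changes, by named arm, as supportive estimates with 95% confidence intervals.
- **Item 5:** carry the same rule to WMFT, Box and Blocks and MAL.
- **Hypotheses:** mark the first as descriptive or supportive.
- **Item 3:** call 2.4 units a between-group difference.
- **Items 2 and 4 and the UCT section:** reconcile the descriptions of the control arm, so that the decisive test and the randomised arms match.

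Making the first null conditional on the between-arm test would also close the ranking gap. Reporting estimates is simpler, and dividing the error rate alone would not supply the missing control.

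The cost is wording. The sample size of 40 and the between-arm figure of 2.4 units at 16 per arm do not change. The sponsor gives up a within-arm significance claim that the design cannot attribute to GRASP.

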#### **5. What is your plan for secondary variable analysis?**

Include the following:

--Secondary outcome(s)/predictor variables, statistical methods/models/tests to be employed, or descriptive summaries as appropriate. If not applicable, please provide explanation.  
--For phase III studies, the power/precision of the study to address the secondary objective(s).

Answer/Response:

The pre- to post intervention changes in the composite Wolf Motor Function Test (WMFT) scores will be analyzed in exactly the same way as the pre to post-intervention change in the

composite FMUE scores, and the same method of analysis will be used to analyze the pre- to post-intervention changes in Box and Blocks Test scores, and the pre- to post-intervention changes in the Motor Activity Log (MAL) scores.

**6. Have you been working with a statistician in designing this protocol?**

Consultation with a professional statistician is highly recommended to ensure good science of the study and facilitate the review process.

Answer/Response:

**YES**

**IF YES, what is their name?**

Answer/Response:

**[name]**

**7. Will data from multiple sites be combined during analysis?**

Answer/Response:

INSTRUCTIONS: IF YES, answer the following questions

NA

## Study Procedures-Biomedical Research

**1. What will be done in this protocol?**

**INSTRUCTIONS:**

This should include everything that will be done as part of this protocol. Do not repeat information that is included in other sections such as Background or Hypothesis sections.

This section should include an indication of which research interventions if any offer a prospect for direct benefit and which interventions (invasive measurements, collection of blood, tissue, data, surveys, etc.) are being done solely to answer a research question and generate generalizable knowledge. If the interventions done solely for research purposes are associated with greater than minimal risk they need to be justified.

Describe and justify any control and experimental arm and include method, dose, and duration of drug administration. Reference any claim of clinical equipoise if applicable.

If you are obtaining specimens or data, provide information regarding the type of specimen/data, amount of specimen needed and how the specimen/data will be obtained and what analysis will be done with the specimen/data.

**Special note for studies with waiver of consent/waiver of documentation of consent:**

Include a statement regarding how subjects will be recruited. For other studies this information is captured in Recruitment does not need to be duplicated in this section.

Answer/Response:

Participants meeting study criteria will be recruited from the population of current and former stroke patients of the University of Virginia Health System.

Prior to consent, potential candidates will be contacted by phone and asked to respond to questions pertaining to eligibility (inclusion/exclusion criteria). For example:

- Do you continue to experience weakness or impaired function in your stroke affected hand?
- Are you able to bend your fingers partially on your stroke affected hand?
- Are you able to move your stroke affected arm and flex your elbow about halfway?
- Is your corrected vision good enough to comfortably watch a TV show for 30 minutes?

The final list of questions will be included in a telephone recruitment scripts that will be submitted for IRB approval prior to use. After pre-screening using the IRB-approved script, candidates will be scheduled for a remotely-administered consent and screening telehealth visit and for a pre-assessment visit at UVA.

**ALL – Remotely-administered consent visit (will last about 45 minutes)**

- Participant will take part in remotely-administered telehealth visit with a study coordinator or a study therapist by phone or HIPAA compliant video conferencing (e.g. a Zoom Health account through UVA).
- Participant will be asked pre-screening questions to verify inclusion and exclusion criteria
- Participant will complete informed consent process and, if consent is provided, sign using DocuSign or alternative institutionally -approved method.

**ALL - Outpatient Visit 1 at UVA: Pre-Assessment (will last about 90 minutes)**

- Blinded study therapist will review consent and re-verify inclusion and exclusion criteria
- Blinded study therapist will administer a battery of hand function tests including: the Fugl-Meyer assessment of UE function (FMUE), the Wolf Motor Function Test (WMFT), the Box and Blocks Test, and the Motor Activity Log (MAL).
- If administration of the test instruments cannot be completed for any reason (e.g. subject becomes fatigued), the participant may be asked to return for an additional visit to complete the procedures. The participant will be provided the normal per-visit stipend for the additional visit.
- Study therapist will take hand measurements for SaeboGlove fitting.
- Subject will be assigned to either the GRASP HEP or the UCT group employing the study randomization procedure and scheduled for remaining visits.

**GROUP 1: GRASP HEP GROUP**

**GRASP HEP Home Visit 1 (will last about 90 minutes)**

- A non-blinded study therapist will conduct a home visit at the patient's residence.
- The therapist will set up the GRASP system and verify the patient's ability to safely and successfully use the system at home.
- The therapist will provide the patient with an appropriately sized SaeboGlove.
- The therapist will assist the patient in learning to don and doff the SaeboGlove with GRASP sensors.
- The patient will practice using the GRASP system for virtual world practice of ADLs and IADLs.

**GRASP HEP Home Visit 2 (will last about 60 minutes)**

- A non-blinded study therapist will conduct a second home visit at the patient's residence.
- The therapist will verify safety of the system setup in the patient's home.
- The therapist will assist the patient in learning to don and doff the SaeboGlove with GRASP sensors.

- The patient will practice using the GRASP system for virtual world practice of ADLs and IADLs.
- If on the study therapist's recommendation, the study PI determines an additional visit is warranted to ensure a patient can safely and successfully use the system at home, an additional home visit will be conducted.

#### **GRASP HEP Independent Practice at Home**

- Participants will be asked to employ the GRASP system for UE practice at home 45 minutes/session, 4 sessions/week over an 8-week period.
- Patients will continue to perform any previously prescribed therapy.
- Once per week during this period, non-blinded study staff will employ an authorized web application on a UVA computing system to remotely monitor de-identified participant data (see Data Security Plan for details) that includes exercise adherence (duration performed), movement repetitions accomplished (exercise reps), and exercise intensity (speed).
- At least once every two weeks, non-blinded study staff will contact the participant by phone or HIPAA compliant video conferencing to collect self-reported adherence data and confirm that no change in medical status has occurred that would impact continued participation.

#### **GRASP HEP Home Visit 3 (will last about 90 minutes)**

- At the end of the 8-week HEP period, a non-blinded study therapist will conduct a home visit at the patient's residence to observe patients' independent use of the system and recover the system hardware.
- Participants will respond to questionnaire-based instruments including the System Usability Scale (SUS), a technology acceptance model (TAM) questionnaire, and a Player Experience of Needs Satisfaction (PENS) questionnaire, as well as participate in a structured interview. These assessments will be audiotaped.

The participant will be encouraged to invite his or her home care provider (e.g. spouse or family member, if applicable) to attend the GRASP HEP visits, so that this individual is able to assist the patient during independent practice.

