**Objectives:**

- Investigate the efficacy of GRASP therapy for recovery of hand function
- Acquire evidence of system usability and user acceptance

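### Usability and acceptance are rated once, at about week 8, and nothing is stated for GRASP participants who withdraw before then, although the plan allows for 20% dropout

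*Combined protocol and SAP*

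**What the plan says.** The second objective is to "Acquire evidence of system usability and user acceptance". The matching hypothesis is general and is not limited to people who complete the programme: "GRASP will be found to be usable and well-accepted by participants who have sustained a stroke".

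The timing is set under GRASP HEP Home Visit 3: "At the end of the 8-week HEP period, a non-blinded study therapist will conduct a home visit at the patient's residence". That visit has three purposes: to watch the participant use the system, to recover the hardware, and to collect the ratings. On the ratings the text reads "Participants will respond to questionnaire-based instruments including the System Usability Scale (SUS", followed by the TAM and PENS questionnaires and a structured interview.

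Statistical Considerations, question 2, also places the questionnaires after 8 weeks. It mentions them directly after the post-assessment visit and does not name a group: "Additionally, subjects will be asked to respond to a set of questionnaire-based instruments including the System Usability Scale (SUS".

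Home Visits 1 and 2 list no usability instrument. The contacts made at least every two weeks cover self-reported adherence and medical status only. No exit questionnaire or early-withdrawal visit is described. On losses, the sample-size justification says: "Note that accounting for a 20% dropout rate, recruitment of a total of 40 subjects provides sufficient power".

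**The concern.** The hypothesis is about people with stroke who are given the system. The ratings, as scheduled, come from those still in the study at about week 8. If some withdraw because they find the system difficult, tiring or unwelcome, their opinions are the ones most relevant to acceptance and the ones most likely to be absent.

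The Background makes this plausible. It notes that intensive repetitive therapy can be dull, tiring or painful, and that adherence is especially hard at home without a therapist. It does not say how often this leads to withdrawal.

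A favourable mean score could then partly reflect who was left to answer. Analysis cannot repair this, because opinions that were not collected cannot be recovered after the trial.

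**Working it through.** **Inputs from the documents.** 40 enrolled and half allocated to GRASP, so 20. Planned dropout is 20% (sample-size justification). Table 1 gives 16 per group at 80% retention.

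**Reproducing the plan's figure.** 20 × (1 − 0.20) = 16, as in Table 1. If the loss is spread evenly over the arms and all falls before Home Visit 3, 20 − 16 = 4 GRASP participants would be unrated.

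**Inputs not in the documents.** No mean, SD or target is given for any usability score, and no rating difference between stayers and leavers. The gaps below are assumptions, in SD units.

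**Formula.** Let p be the share unrated, S the mean among stayers and L the mean that leavers would have given. The mean over everyone is (1 − p)S + pL. The stayers-only mean differs from it by S − [(1 − p)S + pL] = p(S − L).

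| Assumed gap S − L | p = 2/20 = 10% | p = 4/20 = 20% |
|---|---|---|
| −0.5 SD (leavers more favourable) | −0.05 SD | −0.10 SD |
| 0 (loss unrelated to opinion) | 0 | 0 |
| 0.5 SD | 0.05 SD | 0.10 SD |
| 1 SD | 0.10 SD | 0.20 SD |
| 2 SD | 0.20 SD | 0.40 SD |

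The gap is an average over all leavers. If two of four leave for unrelated reasons (gap 0) and two would have rated 1 SD lower, the average gap is 0.5 SD and the bias is 0.10 SD.

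**Comparison with sampling error.** The standard error of a mean of 16 is 1/√16 = 0.25 SD. A bias of 0.20 SD is 0.20/0.25 = 0.8 of that. It would not show in a confidence interval computed from the 16.

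**Bounds without assuming a gap.** On a score assumed to run from 0 to 100, a mean of 70 among 16 raters is compatible with a mean over all 20 from 0.8 × 70 + 0.2 × 0 = 56 to 0.8 × 70 + 0.2 × 100 = 76.

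**The case against.** Several points on the other side are sound.

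A reader might infer that anyone who gives up on GRASP is never asked. The documents do not support this. Home Visit 3 is scheduled for the GRASP group without any condition of continued use, and it also serves to collect the hardware. Someone who stops practising but remains in the study is still due the questionnaires. For those who withdraw, the text is silent; it does not exclude them.

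A reader might also infer that the result is biased upward. That depends on why people leave and how they would have rated the system, and the documents give neither. The 20% covers all causes, including changes in medical status. Under Subjects, question 2, the same figure answers a question that also covers screen failure. Treating all four as people who rejected the device is a worst case, not what the plan expects.

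The consequence is limited, too. Usability has no threshold or test, and no place in the primary or secondary analysis, so no decision rule changes. An end-of-use rating is a legitimate design choice.

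The weekly monitoring of "exercise adherence (duration performed), movement repetitions accomplished (exercise reps), and exercise intensity (speed" gives some information on disengagement. It records use, not opinion, and setting practice time to zero after stopping would count a medical event as rejection. It cannot stand as an acceptance measure free of dropout effects.

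These points narrow the concern to withdrawals before week 8 and remove any firm statement of direction. They leave in place a single late measurement, a planned loss, and no stated attempt to reach those who leave.

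**Conclusion.** The concern holds in this limited form. Followed as written, the plan rates mainly those who stay, while the hypothesis is stated for stroke participants generally. With up to 4 of 20 unrated, the usability result may be selective, and favourably so if poor acceptance drives withdrawal. At 20% missing, the bias is 0 if loss is unrelated to opinion and 0.2 SD at an assumed 1 SD gap; it would be negative if leavers were the more favourable. These figures assume that dropout is even across arms and all occurs before the visit, and they scale down if part of the 20% is screen failure or comes later.

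A secondary point is that the two descriptions of the questionnaires differ. Statistical Considerations, question 2, refers to subjects in general alongside the post-assessment; Home Visit 3 confines them to the GRASP group at home. Neither provides for early withdrawal.

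**What to change.** 1. Amend GRASP HEP Home Visit 3 so that the SUS, TAM, PENS and interview are given when the hardware is recovered, at 8 weeks or at early stop, whichever comes first, and by phone or video if no visit is possible.
2. Report the number rated out of all randomised to GRASP, with reasons for stopping and time on the system beside the scores. Give logged practice time as a supplementary measure of use, not of opinion.
3. Reconcile Statistical Considerations, question 2, with Home Visit 3 on where and to whom the questionnaires are given.

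The cost is about one sentence in the procedures, one correction and a short table. Phone or video contact and a hardware-recovery visit are already in the plan. There are two small drawbacks. Ratings will follow differing lengths of use, which is why time on the system should accompany them. Some who withdraw may also decline to answer, but stating the denominator still lets a reader judge the result.
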